### **2.3.2 Safety population**

The safety population considered for the safety analyses will be the randomized population who actually received at least 1 dose or part of a dose of the study drug (alirocumab or standard of care). Patients will be analyzed according to the treatment actually received (i.e. as-treated treatment group, Standard of Care or Alirocumab).

In addition:

- Non-randomized but treated patients will not be part of the safety population, but their safety data will be presented separately.
- Randomized patients for whom it is unclear whether they took the study drug will be included in the safety population as randomized.
- The treatment group allocation for “as-treated analysis” will be defined as follows:
  - Alirocumab group if IMP injection proportion is  $\geq 50\%$ .
  - SoC group if IMP injection proportion is  $<50\%$ .

IMP injection proportion (%) defined as  $100 \times (\text{Number of IMP injection}) / [(\text{the date of last study treatment administration} - \text{the date of randomization}) / 14 + 1]$

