11.3.2 Safety population

The safety population is defined as the randomized population which actually received at least 1 dose or part of a dose of the study drug, and analyzed according to the treatment actually received.

In addition:

- Non-randomized but treated patients will not be part of the safety population, but their safety data will be presented separately.
- Randomized patients for whom it is unclear whether they took the study drug will be included in the safety population as randomized.
- The treatment arm allocation for “as-treated analysis” will be defined as follows:
 - Alirocumab arm if proportion of IMP injection is $\geq 50\%$.
 - SoC arm if proportion of IMP injection is $<50\%$.
- Proportion of IMP injection (%) is defined as $100 \times (\text{Number of IMP injection}) / [(\text{Date of end of treatment} - \text{Date of randomization})/14 + 1]$

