#### **2.3.1.2 *Per-protocol population***

The per-protocol (PP) population is a subset of the mITT population excluding patients with any major protocol deviations that have significant impact on the primary study objective, analyzed according to the treatment actually received.

Major protocol deviations that do not cause exclusion from mITT population, but have significant impact on the primary study objective are as follows:

- Poor adherence to the study protocol
- IVUS not performed from Week 34 to Week 38 during efficacy treatment period, which is defined as the time from the day of randomization to the last study treatment administration + 21 days.
- Patients with analyzed vessel length less than 10 mm.
- Patients who do not meet the following inclusion criteria.
  - Patient hospitalized for any ACS
  - LDL-C at patient selection (either Friedewald method or direct methods measured at each study site)  $\geq 100$  mg/dL for patients enrolled based on the protocol amendment 1;  $\geq 70$  mg/dL for patients enrolled based on the protocol amendment 2 or later.
  - Patient who undergoes IVUS imaging with at least  $>50\%$  stenosis angiographically within 1 week after the ACS onset. The IVUS imaging should be performed in the culprit vessels with some levels of atherosclerosis/stenosis.
  - Patients aged  $\geq 20$  years old at ACS diagnosis.
- Patients who meet the following exclusion criteria.
  - Patient who has been previously treated with at least one dose of any anti-PCSK9 monoclonal antibody.
  - Patient on LDL apheresis

- Patient who has withdrawn consent before enrolment/randomization (starting from signed informed consent form).

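### The as-treated rule counts alirocumab-exposed patients with an injection proportion below 50% as SoC, and its denominator end date is worded differently in the protocol and the SAP

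*SAP*

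**What the plan says.** The protocol synopsis, protocol 11.3.2 and SAP 2.3.2 all state that the safety population is analysed by treatment received. Each then defines the as-treated group by an injection proportion: 50% or more is alirocumab, less is SoC. The protocol wording is "SoC arm if proportion of IMP injection is" below 50%; the SAP wording is "SoC group if IMP injection proportion is" below 50%. The cut-off and the numerator (number of IMP injections) agree.

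The denominator in both is (end date − randomization date)/14 + 1, but the end date is not worded alike:

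- Protocol: "Date of end of treatment". The protocol has an end-of-treatment visit at Week 36 (Day 253 ± 14 days, section 10.1.1.1.5), but does not say what this date is for a patient who stops early.
- SAP: "the date of last study treatment administration". SAP 2.5.1 defines it as the last administration date on the end-of-treatment CRF page, or missing if unknown. It does not limit the term to injections.

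SAP 2.3.2 also says: "Randomized patients for whom it is unclear whether they took the study drug will be included in the safety population as randomized". SAP 1.5 to 1.7 do not mention the change of end date.

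**The concern.** A table by treatment received should not show someone injected with alirocumab as never exposed, yet a patient below the cut-off is shown that way. The grouping sets the AE denominators (SAP 2.4.5.1), the exposure and compliance summaries (protocol 11.4.1, SAP 2.4.3) and the QOL analysis (SAP 2.3.3). The plan foresees low adherence: protocol 10.3.3 has a discontinuation criterion based on IMP compliance below 50% over 12 weeks.

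The end date then decides whom the rule reaches. SAP 2.3.2 admits patients who received "at least 1 dose or part of a dose of the study drug (alirocumab or standard of care"), and SAP 2.1.4 uses last study treatment administration to close the TEAE period in both groups, so in SoC the term must cover non-injected therapy. SAP 2.4.3.1, by contrast, names the IMP injection when it means that. If continuing statin counted as study treatment, a patient who stopped alirocumab early, perhaps for an adverse event, could be counted in SoC.

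**Working it through.** **Inputs.** The formula from protocol 11.3.2 and SAP 2.3.2; injections every 2 weeks from Week 0 (Day 1) to Week 34 (Day 239), 18 in all; end-of-treatment visit at Day 253.

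Proportion = k / [(end day − 1)/14 + 1], where k is the number of injections.

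**Reading A: the end date is the last injection.** For k consecutive on-schedule doses the denominator is k, so the proportion is 100% for every k. With the last injection at Week w the denominator is w/2 + 1, and the patient falls below 50% only if w > 4k − 2:

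- Weeks 0 and 6: 2/4 = 50.0%, stays
- Weeks 0 and 8: 2/5 = 40.0%, moves
- Three injections, last at Week 10: 3/6 = 50.0%, stays
- Weeks 0, 2 and 12: 3/7 = 42.9%, moves

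Only patients with long gaps move.

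**Reading B: the end date is later.** With k consecutive doses and an end date L days after the last one, the proportion is k/(k + L/14), below 50% only if L > 14k. One dose with end date Day 22 gives 1/2.5 = 40.0% (moves); two doses with end date Day 36 give 2/3.5 = 57.1% (stays). For fixed dates:

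| End date | Denominator | Moves | Stays |
|---|---|---|---|
| Week 34, Day 239 | 238/14 + 1 = 18 | 8/18 = 44.4% | 9/18 = 50.0% |
| Week 36, Day 253 | 252/14 + 1 = 19 | 9/19 = 47.4% | 10/19 = 52.6% |

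A patient who stops after one injection scores 1/1 = 100% under A and 1/19 = 5.3% under B at Week 36.

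**Which reading the text favours.** Protocol 11.4 leaves detail to the SAP, and the SAP uses last administration. Full adherence to Week 34 scores 18/18 = 100% under A but 18/19 = 94.7% with a Week 36 date. The SAP 2.4.3.1 exposure table has categories below 12 weeks. These allow at most 6 injections (the sixth given up to 7 days early), and 6/19 = 31.6%, so with a Week 36 date those rows would be empty in the alirocumab group. All this points to A, but no passage says so.

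**Size, for illustration.** The Japanese Phase 3 study had 4.9% IMP discontinuation for TEAEs on alirocumab over 52 weeks (protocol section 4). Assuming a constant rate and that it carries over to this different population, stops before the Week 18 (tenth) dose are 1 − 0.951^(18/52) = 1.7%. That is about 1.7 per 100 moved under a Week 36 date; the range for AE stops is 0 to 4.9 per 100. Under A, on-schedule AE stoppers do not move.

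Assuming 100 treated per arm, one moved patient with an event raises a SoC rate p by (1 − p)/101: 0.99 points at p = 0, 0.87 at 12.5% and 0.17 at 83.3% (the last two are that study's placebo SAE and TEAE rates). The shift approaches one point only for events rare in SoC.

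**The case against.** The 50% cut-off is pre-specified identically in both documents. The SAP date is defined, and its generic wording has an ordinary explanation: the same term must serve SoC patients, who have no injection date. Read as the last injection, it leaves every on-schedule early stopper in alirocumab. Where treatment is interrupted for a suspected AE, restart requires that study treatment was judged unlikely to be responsible (protocol 10.3.1), so gaps of that kind should seldom hide a drug-related event. AE discontinuation is plotted as randomized (SAP 2.2), and IMP-related TEAEs and SAEs have their own tables (SAP 2.4.5.1). A SAP clarification alone would settle the date.

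Most of this stands, and it limits the size. It does not justify the rule, since Weeks 0 and 8 still give 40% on the most favourable reading. Nor is the date fully settled: SAP 2.5.1 is not restricted to injections, and the theoretical date in SAP 2.5.3 for a missing date is stated for exposure duration and compliance, not for this allocation.

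The per-protocol analysis is a fair counterpoint. It too is "analyzed according to the treatment actually received" and has no grouping rule of its own. But SAP 2.3.1.2 excludes patients without IVUS in Weeks 34 to 38 within 21 days of last administration. On the injection reading the last injection is then at Week 31 or later. Falling below 50% would need at most 8 injections with the last at Week 31 (8/16.5 = 48.5%), or at most 9 with the last at Week 36 (9/19 = 47.4%). Such patients are obvious candidates for the exclusion "Poor adherence to the study protocol", although that term is undefined.

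**Conclusion.** The rule conflicts with the stated principle under every reading of the end date, because it can show an alirocumab-exposed patient as unexposed. The number affected cannot be derived from the documents. On the better-supported reading it is limited to patients with long dosing gaps and may be zero. With a Week 36 date it would include on-schedule patients stopping after 1 to 9 injections. The reach is the as-treated safety, exposure/compliance and QOL tables; safety is descriptive and the primary analysis is as randomized.

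Three stronger conclusions might be inferred and are not supported:

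- **That the end date is defined in neither document.** SAP 2.5.1 defines the SAP term. The protocol term is undefined, and the SAP term is not limited to injections.
- **That patients stopping for adverse events will be moved to SoC.** If they were on schedule, this happens only with an end date well after the last injection, which the text disfavours.
- **That poor compliers disappear from the exposure summary.** Protocol 11.4.1 presents IMP exposure for the alirocumab arm, but SAP 2.4.3 summarizes by actual treatment across the safety population. On the SAP text their injections would appear under SoC, which is mislabelling rather than removal.

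**What to change.** In the protocol synopsis, protocol 11.3.2 and SAP 2.3.2, replace the 50% rule for the safety, exposure/compliance and QOL analyses with: *Patients who received at least one full or partial alirocumab injection are analysed in the alirocumab group; patients with unclear intake are analysed as randomized; all others are analysed in SoC.* This needs no end date.

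Add a listing of patients whose as-treated group differs from the randomized arm, with number and dates of injections. If the injection proportion is kept, report it descriptively, with the last IMP injection date as the end date in both documents.

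Do not extend the ever-injected rule to the per-protocol efficacy analysis: a SoC patient injected once in error would count as alirocumab for plaque change. SAP 2.3.1.2 should state its own grouping.

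Cost: one sentence in three places, a simpler flag and one short listing. The protocol wording needs an amendment with IRB/IEC approval (protocol 15). In the safety tables a SoC patient injected once in error will count as alirocumab; the listing makes this visible.

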### **2.3.3 Quality-of-life population**

The analyses of QOL will be performed on all randomized and treated patients (safety population) with a baseline and at least 1 matching post-baseline evaluation for any of the 5 dimensions. Patients will be analyzed according to the treatment actually received.

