11.3.3 Quality-of-life (QOL) population

The analyses of QOL will be performed on all randomized and treated patients (safety population) with a baseline and at least 1 matching post-baseline evaluation for any of the 5 dimensions.

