### ***EQ-5D utility score***

The raw value and the absolute change from baseline of the utility score will be summarized using mean, median, Q1, Q3, SD, minimum, and maximum for each post-baseline visit. Cumulative distribution functions for the absolute change in utility score from baseline will be displayed by treatment groups, at Week 4, Week 12, Week 24, and Week 36.

The absolute change from baseline in utility score to Week 4, Week 12, Week 24, and Week 36 will be analyzed using a MMRM model with fixed categorical effects of treatment group, randomization strata as per the registration center, treatment-by-time point interaction, strata-by-time point interaction, as well as, the continuous fixed covariates of baseline value and baseline value-by-time point interaction.

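### The only planned between-arm EQ-5D model groups patients by treatment received, set by a post-randomization injection rule, so its contrast is not a randomized comparison

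*SAP*

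**What the plan says.** SAP 2.3.3 takes the safety population, limited to those who have both a baseline assessment and a later one to match it on any EQ-5D dimension. It then fixes the grouping: "Patients will be analyzed according to the treatment actually received". Protocol 11.3.3 ties quality of life to the same safety population, which Protocol 11.3.2 analyzes by treatment received.

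The EQ-5D utility part of SAP 2.4.7 gives the model: "The absolute change from baseline in utility score to Week 4, Week 12, Week 24, and Week 36 will be analyzed using a MMRM model". Its terms are treatment group, randomization strata, their interactions with time point, and baseline. Protocol 11.4.5 describes it as the MMRM already used for the lipid endpoints with several post-baseline visits. Those lipid models run in the mITT population, which SAP 2.3.1.1 analyzes by randomized arm. No as-randomized EQ-5D analysis is specified in either document.

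The received arm comes from an injection proportion in SAP 2.3.2. It is 100 times the number of injections, divided by the days from randomization to an end date over 14, plus 1. A patient goes to alirocumab at 50% or more; the other branch reads "SoC group if IMP injection proportion is" below 50%. The SAP's end date is "the date of last study treatment administration"; Protocol 11.3.2 has "Date of end of treatment".

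**The concern.** The injection proportion is known only after randomization and depends on how a patient tolerates and attends treatment. Using it to decide who counts as alirocumab and who counts as SoC gives up the balance that randomization provides. In practice movement is one way: alirocumab patients can fall below 50%, while SoC patients are not given the product and other anti-PCSK9 antibodies are prohibited (Protocol 8.8).

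A link to health status is plausible. Protocol 10.3.1 describes temporary stops for suspected adverse events, and Protocol 10.6.2 interrupts injections on suspicion of an allergic event. A moved patient's scores all count as SoC, including any recorded while on alirocumab. EQ-5D is patient-reported and the trial is open-label, so this comparison has little protection beyond randomization. What is at stake is the meaning of the EQ-5D difference, not the primary result.

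**Working it through.** **Plan's own figure.** The documents give no EQ-5D effect, SD, power or sample size. The stated primary sample size reproduces: a difference of 8 with SD 15 and 75 per arm gives 90.06% power by a two-sample t-test, and 150/(1 − 0.25) = 200. It is used here only for the 100 randomized per arm.

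**Who is moved.** The planned schedule is 18 injections, every two weeks from Week 0 to Week 34 (Protocol 6.1 and 10.1.1).

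Case 1: injections skipped, dosing continues. The end date is then late under any reading, as these examples with the last-injection date show.
- Weeks 0, 2 and 12: 3/(84/14 + 1) = 3/7 = 43%, moved to SoC.
- Last injection at Week 34: the denominator is 238/14 + 1 = 18. Eight injections give 8/18 = 44.4%, moved; nine give 50.0%, not moved.

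Case 2: injections on schedule, then stopped. The result depends on which drug's last date is used.

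| Injections (last at) | End date = last injection | End date = statin, Week 34 (denominator 18) | End date = statin, Week 36 (denominator 252/14 + 1 = 19) |
|---|---|---|---|
| 3 (Week 4) | 100% | 16.7% | 15.8% |
| 8 (Week 14) | 100% | 44.4% | 42.1% |
| 9 (Week 16) | 100% | 50.0% | 47.4% |
| 10 (Week 18) | 100% | 55.6% | 52.6% |

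With the last injection as end date, nobody who stops after on-schedule dosing is moved, however early the stop. With the last statin date, patients are moved if their last injection is at Week 14 or earlier (statin to Week 34) or Week 16 or earlier (statin to Week 36). On-schedule patients who stop later stay in alirocumab under every reading.

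**Which reading the text supports.** For the statin reading:
- SAP 2.3.2 counts standard of care as study drug.
- SAP 2.1.4 applies the last study treatment date to both groups.
- SAP 2.4.3.1 names the IMP injection date where injections are meant.
- The protocol synopsis describes this arm's treatment as statin plus alirocumab.

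For the injection reading, Protocol 10.3.2 defines permanent discontinuation by the IMP. SAP 2.5.1 takes the last administration date from the end-of-treatment form without naming the drug. The text does not settle it.

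**Size if patients are moved.** Assumptions, none from the documents: no true effect, and k of 100 alirocumab patients moved, each with utility lower by D.
- As randomized: −kD/100.
- As received: +kD/(100 + k).
- Shift: kD/100 + kD/(100 + k).

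| k | D | As randomized | As received | Shift |
|---|---|---|---|---|
| 2 | 0.05 | −0.0010 | +0.0010 | 0.0020 |
| 5 | 0.10 | −0.0050 | +0.0048 | 0.0098 |
| 10 | 0.10 | −0.0100 | +0.0091 | 0.0191 |
| 10 | 0.20 | −0.0200 | +0.0182 | 0.0382 |

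If moved patients scored higher by D, each shift would have the opposite sign.

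**The case against.** The strongest case against has four parts.

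**The rule may move few patients.** A reader might infer that anyone who stops injections is credited to SoC. The documents do not support that: with a last-injection end date, an on-schedule patient who stops keeps 100%. This stands and limits the point to the two cases above. It does not remove it, because frequent skippers are moved under either reading. The protocol anticipates such patients: Protocol 10.3.3 makes compliance below 50% over 12 weeks a discontinuation criterion.

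**The size is assumed and may be small.** This stands. The illustration compares simple means, while the plan fits a baseline-adjusted MMRM by visit window. The study flow chart's EQ-5D footnote and Protocol 10.3.4 place the last questionnaire of patients leaving before Week 24 soon after they stop, so they supply few later scores. With an assumed SD of 0.15 to 0.20 and 100 per arm, the standard error is SD × √(2/100), or 0.021 to 0.028. The 0.0098 shift is under half of that.

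**EQ-5D is exploratory.** Protocol 9.3 lists it among other endpoints, Protocol 11.4.4 calls those variables exploratory, and it is in no objective and outside the testing hierarchy. This stands and bounds the consequence, but does not justify as-received grouping for the only EQ-5D comparison planned.

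**As-received grouping is not unique to EQ-5D.** A reader might say that every other efficacy model uses the randomized arm. That is not so: the supportive per-protocol analyses of IVUS endpoints use treatment received (SAP 2.3.1.2, 2.4.4.1 and 2.4.4.2). They sit beside as-randomized analyses, which EQ-5D lacks. Adjusting for the strata is also not a fault, since statin use at ACS onset is a legitimate baseline covariate under either grouping.

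**Conclusion.** The point holds as a cheap improvement. The only planned between-arm EQ-5D model compares groups formed partly by post-randomization behaviour, so its contrast is not a randomized one.

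How many patients are affected cannot be determined from the documents, because it depends on skipping patterns and on an end date that is not pinned down. Under the stated assumptions the shift is about 0.002 to 0.038 in utility. It is tempting to say the analysis is biased toward alirocumab. The documents do not establish this: it requires moved patients to score lower, and Protocol 10.3.3 also lists reasons for stopping that need not reflect health, such as patient or sponsor request. Primary and key secondary conclusions are unaffected, because those analyses use the mITT population by randomized arm.

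**What to change.** - In SAP 2.3.3 and 2.4.7, analyze the EQ-5D items, the utility score and the MMRM by randomized arm, in randomized patients with a baseline and at least one post-baseline evaluation. Keep an as-received version at most as supportive.
- Record this as a departure from Protocol 11.3.2 and 11.3.3, which tie quality of life to the as-treated safety population.
- Keep as-received grouping for adverse events, laboratory values and vital signs.
- In SAP 2.3.2 and 2.5.1, state which drug's last date ends the injection-proportion denominator, and reconcile the SAP wording with Protocol 11.3.2. This matters for the safety tables as well.

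Cost: an SAP sentence on grouping, the date clarification, a changed treatment variable in the quality-of-life programs, and a documented departure from the protocol. No sample size or power figure changes.

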## **2.4 STATISTICAL METHODS**

### **2.4.1 Demographics and baseline characteristics**

Parameters described in [Section 2.1.1](#) will be summarized by treatment group and overall using descriptive statistics.

Continuous data will be summarized using the number of available data, mean, standard deviation (SD), median, minimum, and maximum for each treatment group. First quartile (Q1) and third quartile (Q3) will be also provided for baseline IVUS parameters, lipid parameters, HbA1c, hs-CRP. Categorical and ordinal data will be summarized using the number and percentage of patients in each treatment group.

Unless otherwise specified, parameters will be summarized on the randomized population and mITT population analyzed in the treatment arm to which they were randomized. Similar analyses

will be done on the PP population (respectively safety population) in the treatment arm to which they are actually received if the size of the PP population (respectively safety population) is different (>10%) from the size of the mITT population (respectively randomized population) for any treatment group. In the randomized population and mITT population, parameters will also be summarized within each randomization strata as per the registration center and within each diabetic status at baseline.

All reported patient's medical and surgical history and all ongoing reported patients' these histories at the start of study will be presented by primary SOC and HLT. The tables will be sorted by SOC internationally agreed order and decreasing frequency of HLT based on the overall incidence across treatment groups. In addition all medical history of specific interest will be presented by treatment group.

P-values comparing the 2 treatment groups on demographic characteristics, disease characteristics and other baseline characteristic data will be provided for descriptive purpose, as a screening tool, using the Fisher exact test for categorical data and Wilcoxon rank sum test for continuous data.

No specific description of the safety parameters will be provided at baseline. If relevant, the baseline values will be described along with each safety analysis.

